7.1.2.2 Alternative Estimand

One alternative estimands for OS is defined as below, arising from changes in strategy for handling some intercurrent events to “hypothetical.” This analysis is intended to “factor out” the

effects of non-protocol anti-cancer therapy on overall survival. Shaded cells differ from primary estimand.

Estimand Attribute ¹	Alternate definition	
Population	Subjects randomized into the study intended to include patients with advanced hepatocellular carcinoma who have not received previous systemic anticancer therapy.	
Endpoint	Duration of overall survival	
Intercurrent event(s)	Event	Strategy
	Receipt of assigned study treatment	Treatment policy
	Receipt of systemic non-protocol anti-cancer medications	Hypothetical
	Receipt of local liver-directed non-protocol anti-cancer medications	Hypothetical
	Lost to follow-up	Hypothetical
Population summary	Difference in survival functions between treatment conditions	

¹See Appendix E for estimand terminology

7.1.2.3 Primary Definition

For the primary analysis directed toward the primary estimand (analysis ID OS-EP-1), duration of OS is defined as the time from randomization to death due to any cause. For subjects who are not known to have died at the time of data cutoff and are permanently lost to follow-up, duration of OS will be right censored at the earlier of the following dates: date the subject was last known to be alive or date of full withdrawal of consent (including survival follow-up), or date of data cutoff.

$$\text{OS (months)} = (\text{earlier of date of death or censoring} - \text{date of randomization} + 1)/30.4375$$

7.1.2.4 Hypothesis

The hypotheses to be evaluated in the analysis of the OS are:

$$H_0: S(t)_{\text{cabozantinib + atezolizumab}} = S(t)_{\text{sorafenib}}$$

$$H_A: S(t)_{\text{cabozantinib + atezolizumab}} \neq S(t)_{\text{sorafenib}}$$

where $S(t)_{\text{cabozantinib + atezolizumab}}$ and $S(t)_{\text{sorafenib}}$ are the survivor functions for OS for the experimental and control arms, respectively.

7.1.2.5 Primary Analysis

The timing of this analysis is event-driven and it will be conducted after at least 368 deaths (overall survival events) have been observed in the experimental and control arms in the ITT population. The actual number of events at the time of analysis may be higher than 368 due to

the logistics of estimating event counts in an ongoing multicenter clinical study and predicting cutoff dates for analysis.

The hypothesis testing between the experimental arm (cabozantinib + atezolizumab) compared to the control arm (sorafenib) will be performed using a 2-sided stratified log-rank test. Please see Section 7.2 for details regarding the allocation of overall Type I error (α -level). The stratification factors are as described in Section 2.4 and the values used for analysis will be those recorded in the IRT.

Additionally, up to two interim analyses of OS are planned at approximately the 33% (conditional on positive PFS endpoint inference) and 66% information fractions. The critical p-values (and observed HR) for testing these interim hypotheses will be based on Lan-DeMets O'Brien-Fleming alpha-spending function. The overall α to be spent on testing the duration of OS via the use of a spending function will as described in Section 7.2. The actual critical values for each OS analysis will depend upon the true number of events observed at conduct of each analysis. Details are provided in Section 7.3.

The median duration of OS along with the associated $(1-\alpha)$ % and 95% confidence intervals (CI) for each study treatment arm will be estimated using the Kaplan-Meier method. The stratified hazard ratio (HR) along with the associated $(1-\alpha)$ % and 95% CIs will be estimated using a Cox proportional-hazard model with treatment group as the independent variable using the same stratification factors as were used for the log-rank test.

If at any OS analysis (interim or primary) the p-value for the stratified log-rank test is less than the critical value for rejecting the null hypothesis and the HR (λ cabozantinib + atezolizumab/ λ sorafenib) is < 1 , the null hypothesis of no difference between the two study treatment arms will be rejected and it will be inferred that duration of OS is greater in the experimental arm (cabozantinib + atezolizumab) compared to the control arm (sorafenib).

The unstratified versions of all the above analyses will also be conducted.

7.1.2.6 Supportive Analyses

A supportive analysis (OS-EA1-1) directed at the alternative estimand will be conducted in the experimental and control arms in the ITT population. In this analysis a subject receiving non-protocol systemic or local-liver directed anticancer therapy (medications) will be right censored at the first start date of such subsequent anticancer therapy. Summaries will be provided as for

the primary analysis of OS.

7.1.2.7 Exploratory Analyses

Exploratory analyses of the effect of baseline characteristics, stratification factors, and other variables on OS may be conducted if necessary, using Cox regression models and subgroup analyses performed employing Kaplan-Meier methods.

An exploratory analysis of OS between the single-agent cabozantinib and sorafenib arms in the ITT population will also be performed following the same methodology as in Section 7.1.2.5.

7.2 Control of Type I Error

Inflation of Type 1 error associated with testing of multiple-primary endpoints and a secondary efficacy endpoint (PFS between single-agent cabozantinib and control) will be controlled by a modified Bonferroni procedure and a parallel gatekeeping method (FDA 2017). Initially, the study-wise 2-sided alpha of 5% will be unequally allocated between primary endpoints PFS (1%) and OS (4%). The secondary PFS endpoint will be tested at the 1% level only if the primary PFS test is successful. If the null hypotheses are rejected for both the primary and secondary PFS endpoints, the 1% alpha for PFS will be reallocated to OS, allowing it to be tested at the 5% level.

Two interim analyses of OS are planned at the 33% and 66% information fractions (the first interim will coincide with the primary analysis of PFS and will be performed only if the null hypothesis for PFS is rejected analysis and is expected to occur at approximately the 33% information fraction). Type 1 error associated with interim analyses will be controlled using Lan-DeMets O'Brien-Fleming (LD-OF) alpha-spending functions based upon a 4% total alpha allocation for OS. However, if the null hypotheses are rejected for both the primary and secondary PFS endpoints, the 1% alpha for PFS will be reallocated to OS per the fallback method. As a consequence, the final OS analysis will employ critical values from the spending function at 5% level. The alpha level of the interim analysis at 66% will be dependent on the timing of the interim analysis. It can be conducted at 5% alpha level only if it occurs after the null hypothesis for the secondary PFS is rejected. (see Section 7.3).

All other statistical evaluations of efficacy will be considered exploratory.

7.3 Interim Analyses

The number of events required to evaluate OS is based upon assumptions currently available and provides high power to detect the smallest clinically meaningful difference in OS under these assumptions. However, as there is uncertainty in the assumptions, interim analyses provide an opportunity to stop the trial early if the treatment benefit of the experimental arm is larger than expected, potentially allowing the new regimen to become available sooner to this patient population.

Two interim analyses (IA) of OS are planned at approximately the 33% (IA1) and 66% (IA2) information fractions based on a total alpha of 4%. However, if the null hypotheses are rejected for both the primary and secondary PFS endpoints, the 1% alpha for PFS will be reallocated to OS per the fallback method (FDA Guidance for Industry: Multiple Endpoints in Clinical Trials (draft), 2017). As a consequence, the OS analyses may employ critical values from the spending function at the 5% level if performed after the null hypothesis for the secondary PFS is rejected.

Table 11: Details and Boundaries for the Interim and Final Analyses

		Critical Values for Testing OS		
OS alpha total	4.0%		5.0% ^a	
OS analysis information fraction	Critical p-value	HR to reject	Critical p-value	HR to reject
33% ^b (IA1)	≤ 0.00011	≤ 0.478	≤0.00021 ^b	≤ 0.482 ^b
66% (IA2)	≤ 0.00867	≤ 0.701	≤ 0.01202	≤ 0.705
100% (final)	≤ 0.03728	≤ 0.794	≤ 0.04626	≤ 0.797

HR, hazard ratio; NA, not applicable; OS, overall survival.

^a Analyses of OS will be conducted at 5% alpha level only if the null hypotheses for both the primary and secondary PFS endpoints are rejected prior to testing OS.

^b OS will not be tested at the 33% information fraction unless the null hypothesis for PFS has been rejected.

Rejection of the null hypotheses for OS at the first interim analysis at about 33% information is not expected: it is designed primarily as an administrative analysis to coincide with the primary analysis of PFS and will be performed only if the null hypothesis for PFS is rejected.

Due to logistical considerations in event ascertainment and operational planning and conduct, the actual analyses may include more or fewer events than the target information fractions. The

actual critical values employed at the interim and final analyses of OS will depend upon the actual information fraction at the time of the analyses.

Should the timing of the first interim analysis of OS (IA1) trend towards an information fraction much higher than expected (e.g. due to faster-than-expected deaths or slower-than-expected PFS events), the interim analyses of OS will be conducted as follows.

OS IA1 IF	Proceed as	Rationale
<50%	perform IA1 and IA2 as planned	similar conditions to original plan
50 to <66%	
 • perform IA1 at time of primary PFS, irrespective of whether PFS null hypothesis is rejected or not • Conduct IA2 to 80% IF (instead of 66%) 	
 • Higher than expected information for OS negates administrative nature of the analysis. • Preserves two IA as planned with reasonable intervals between them
≥66%	perform a single IA at 66% IF, irrespective of timing or results of primary PFS analysis.	Information fraction meets or exceeds that of planned analysis at 66%

An interim analysis of secondary PFS is planned contemporaneously with the primary PFS analysis and will be conducted only if the null hypothesis for primary PFS is rejected. It is anticipated to be at approximately 67% information fraction based on a total alpha of 1%.

If null hypothesis is rejected for a given endpoint at interim analysis (secondary PFS or OS), no subsequent testing of that endpoint will be performed.

Interim analysis of primary PFS and futility analyses of PFS or OS are not planned.

7.4 Secondary Efficacy Endpoint

7.4.1 Progression Free Survival (PFS) per BIRC between Single-Agent Cabozantinib and Control Arms

The secondary efficacy endpoint for this study is PFS per BIRC between single-agent cabozantinib and the control arms in the ITT population. The timing of this analysis is event-driven, and it will be conducted after at least 283 events have been observed in the two arms. Formal hypothesis testing is planned for this endpoint following the same methodology as outlined in Section 7.1.1.6. One interim analysis of secondary PFS is planned, to be

contemporaneous with the primary PFS analysis, at approximately the 67% information fraction (Section 7.3)

A supportive analysis of PFS per INV will also be performed on the ITT population.

7.5 Additional Endpoints

Each exploratory endpoint will be analyzed using an appropriate two-sided statistical test without adjustment for multiplicity unless specified otherwise. Statistical results for exploratory endpoints will be considered supportive. Exploratory analyses will be performed on the PITT and ITT populations unless specified otherwise.

7.5.1 Objective Response Rate (ORR) by BIRC

For each subject, best overall response (BOR) is defined as the best tumor assessment category as determined per RECIST 1.1 by BIRC that occurs through the first overall time point response of PD and prior to any of the censoring events defined for the primary analysis of PFS as described in Section 7.1.1. Tumor assessment categories are ranked as: confirmed complete response (CR), confirmed partial response (PR), stable disease (SD), progressive disease (PD) and not evaluable (NE). To be classified as confirmed CR or confirmed PR, confirmation must have occurred on a subsequent visit that is ≥ 28 days after the response was first observed. To be classified as SD, at least one overall time point response of SD must be documented ≥ 21 days after randomization. The ORR is defined as the proportion of subjects with a BOR of confirmed CR or confirmed PR.

Point estimates of ORR for each study treatment arm, the difference in ORR between the two study treatment arms and associated $(1-\alpha)$ % confidence intervals will be provided. The odds ratio and associated $(1-\alpha)$ % confidence intervals will also be presented. The 2-sided CIs for the point estimate will be calculated using exact methods. The 2-sided CIs for the difference in ORR between the two study treatment arms and for the odds ratio will be calculated using asymptotic methods. All summaries for ORR will be provided for the PITT and ITT Populations

Waterfall plots displaying maximum percent tumor reduction since baseline in target lesions will be generated for tumor assessment data per BIRC.

These plots will include subjects with a tumor assessment at baseline and at least one post-baseline visit. For each subject, data on or after the progression/censoring date of the respective PFS analyses described in Section 7.1.1 will be excluded from the waterfall plots.

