4.2. Inclusion Criteria

1. Histological or cytological diagnosis of HCC or clinical diagnosis of HCC in cirrhotic patients by multiphase imaging using CT or MRI per the American Association for the Study of Liver Diseases (AASLD) (Marrero et al 2018) or European Association for the Study of the Liver (EASL 2018) guidelines.

Note: Sites must receive Sponsor accreditation for imaging-based diagnosis of HCC prior to implementing this methodology. In addition, subjects who do not meet the AASLD or EASL guidelines for imaging diagnosis of HCC or who do not have cirrhosis must have histological or cytological diagnosis of HCC.

2. The subject has disease that is not amenable to a curative treatment approach (eg, transplant, surgery, ablation therapy) or locoregional therapy (eg, TACE).
3. The subject is receiving antiviral therapy per local standard of care if the subject has active HBV infection (defined by HBsAg positive); the subject must have HBV DNA < 500 IU/mL.
4. Measurable disease per RECIST 1.1 as determined by the Investigator.
5. Barcelona Clinic Liver Cancer (BCLC) stage Category B or C ([Appendix I](#)).
6. Child-Pugh Score of A ([Appendix J](#)).
7. Recovery to baseline or ≤ Grade 1 per Common Terminology Criteria for Adverse Events (CTCAE) v5 from toxicities related to any prior treatments, unless AE(s) are clinically nonsignificant and/or stable on supportive therapy as determined by the Investigator.
8. Age eighteen years or older on the day of consent.
9. Eastern Cooperative Oncology Group (ECOG) performance status of 0 or 1.

10. Adequate organ and marrow function, based upon meeting all of the following laboratory criteria within 14 days prior to randomization:

- a. Absolute neutrophil count (ANC) $\geq 1500/\mu\text{L}$ ($\geq 1.5 \times 10^9/\text{L}$) without granulocyte colony-stimulating factor support within 2 weeks before screening laboratory sample collection.
- b. White blood cell (WBC) count $\geq 2000/\mu\text{L}$ ($\geq 2.0 \times 10^9/\text{L}$).
- c. Platelets $\geq 60,000/\mu\text{L}$ ($\geq 60 \times 10^9/\text{L}$) without transfusion within 2 weeks before screening laboratory sample collection.
- d. Hemoglobin $\geq 9 \text{ g/dL}$ ($\geq 90 \text{ g/L}$) without transfusion within 2 weeks before screening laboratory sample collection.
- e. Hemoglobin A1c (HbA1c) $\leq 8\%$ within 28 days before randomization (if HbA1c results are unavailable [eg, hemoglobin variant], a fasting serum glucose $\leq 160 \text{ mg/dL}$)

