After baseline, target lesions should have the actual size documented, if possible, even if the lesions become very small. If in the opinion of the radiologist the lesion has likely disappeared, 0 mm should be recorded. If the lesion is present but too small to measure, an indicator for 'too small to measure' should be included in source documents.

For target lesions, measurements should be taken and recorded in metric notation.

Nontarget lesions are to be assessed qualitatively (present, resolved, or unequivocal progression) and new lesions, if any, are to be documented separately.

At each evaluation, progression status is to be determined based upon the time point status for target lesions, nontarget lesions, and new lesions.

Finding of new lesions should not be attributable to differences in scanning technique, change in imaging modality or findings thought to represent something other than tumor. Necrosis of pre-existing lesions as part of a response to treatment should be excluded before defining a 'new' cystic lesion. A lesion identified on a follow-up study in an anatomical location that was not scanned at baseline is considered a new lesion. If a new lesion is equivocal because of its small size, repeat scans need to confirm there is definitely a new lesion, and progression should be declared using the date of the initial scan.

Time point progression cannot be based solely on bone scan findings. Bone scans are to be used to direct corroborative imaging with CT/MRI if necessary. These CT/MRI findings will be used for the determination of progression.

TIME POINT RESPONSE CRITERIA

Target Lesion Time Point Response (TPR)	
Complete Response (CR)	Disappearance of all target lesions. All pathological lymph nodes (whether target or non-target) must have reduction in short axis to < 10 mm.
Partial Response (PR)	At least a 30% decrease in SoD of target lesions, taking as a reference the baseline SoD.
Stable Disease (SD)	Neither sufficient shrinkage to qualify for PR nor sufficient increase to qualify for PD.
Progressive Disease (PD)	At least a 20% increase in the SoD of target lesions, taking as a reference the smallest (nadir) SoD since (and including) baseline. In addition to the relative increase of 20%, the SoD must also demonstrate an absolute increase of at least 5 mm.
Not Applicable (NA)	No target lesion identified at baseline.

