CR, complete response; PR, partial response; SD, stable disease; PD, progressive disease; TPR, time point response; UE, unable to evaluate; NA, not applicable (no such lesions at screening); Any, CR, PR, SD, PD, NA, or UE.

The overall response at a given time point does not depend upon the overall response assigned at any prior or subsequent time point (ie, confirmation requirement are not considered when assigning time point responses).

* Subjects with an overall response of CR or PR must have a follow-up tumor assessment performed no less than 4 weeks after the criteria for response are first met (this may be performed at the next scheduled tumor assessment). However, the presence, absence, or status at this follow-up assessment is not considered when assigning a time point response at prior time points.

** If a lesion disappears and reappears at a subsequent time point it should continue to be measured. However, the subject's response at the point in time when the lesion reappears will depend upon the status of his/her other lesions. For example, if the subject's tumor had reached a CR status and the lesion reappeared, then the subject would be considered PD at the time of reappearance. In contrast, if the tumor status was a PR or SD and one lesion which had disappeared then reappears, its maximal diameter should be added to the sum of the remaining lesions for a calculated response.

Furthermore, in order to identify potential delayed immune-mediated tumor response, subjects with an overall response of PD per RECIST 1.1 who continue with study treatment because of evidence of clinical benefit as assessed by the investigator should have a follow-up tumor assessment no less than 4 weeks after the initial PD criteria were met. This may be performed at the next scheduled tumor assessment. However, the presence, absence, or status at this follow up assessment is not considered when assigning a time point response at prior time points.

Confirmation

The main goal of confirmation of objective response is to avoid overestimating the response rate observed. For subjects with an overall response of PR or CR at a given time point, a follow-up tumor assessment must be performed no less than 4 weeks after the criteria for response are first met. This may be performed at the next scheduled tumor assessment.

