7.1.1 Duration of Progression-Free Survival (PFS)

7.1.1.1 Definitions and Conventions

Only adequate tumor assessments (ATAs) will be considered in the determination of radiographic progression and censoring dates. For the purpose of this study, an ATA is defined as one that results in a time point assignment of complete response, partial response, stable disease/(non-CR, non-PD), or progression.

The recorded date of radiographic progression is the date of the tumor assessment visit at which progression is declared. If multiple scan dates are associated with a tumor assessment visit, the earliest scan date within the set will be chosen as the progression date.

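### SAP 7.5.1 classifies an unconfirmed CR or PR with no stable-disease time point as PD or NE, although the tumour shrank

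*SAP*

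**What the plan says.** SAP 7.5.1 ranks BOR as confirmed CR, confirmed PR, SD, PD and NE. It counts assessments up to the first PD and before any event that censors the primary PFS analysis.

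- For a confirmed response, "confirmation must have occurred on a subsequent visit that is ≥ 28 days after the response was first observed".
- For SD, "To be classified as SD, at least one overall time point response of SD must be documented", with a minimum of 21 days from randomization.
- For the rate itself, "The ORR is defined as the proportion of subjects with a BOR of confirmed CR or confirmed PR".

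SAP 7.5.2 applies the same method to the investigator's assessments.

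Protocol Appendix E defines the time point categories. A target-lesion PR is "At least a 30% decrease in SoD of target lesions" relative to baseline. The notes to its overall-response table say that "confirmation requirement are not considered when assigning time point responses". The appendix leaves BOR to the statistical analysis.

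SAP 7.1.1.1 lists the results that make a tumour assessment adequate. The list ends with "stable disease/(non-CR, non-PD), or progression", so Non-CR/non-PD stands beside SD there.

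**The concern.** A response that is never confirmed has to go somewhere in the BOR classification. The natural place is SD: the subject did at least as well as stable disease, but the stronger category was not established. SAP 7.5.1 closes that route, because SD needs a scan that is itself SD. A subject whose scans show a response and then progression, or a response and then nothing evaluable, drops past SD to PD or NE.

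The per-subject ordering then contradicts the data. A subject with a decrease of at least 30% ranks below one whose tumour did not change appreciably. In the PR-then-PD case the waterfall plot in the same section would show the shrinkage while BOR said PD. Two programmers could also differ, one following the sentence and one following the sense of the ranking.

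**Working it through.** No sample size, event count or error rate is involved, so the check is to apply the rule as written to sequences of scans.

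**Inputs**
- Categories, SD condition, 28-day confirmation rule and ORR definition: SAP 7.5.1.
- Time point categories, and the statement that they do not depend on confirmation: Protocol Appendix E. A PR that is not repeated stays PR and is not recoded to SD.
- Scan schedule: every 6 weeks, ± 7 days, through Week 49 (Protocol 5.8.6.2).

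**Timing.** The earliest on-schedule first scan is 42 − 7 = 35 days after first dose, beyond the 21-day minimum. The closest first and second scans are (84 − 7) − (42 + 7) = 77 − 49 = 28 days apart, which meets the confirmation interval. For on-schedule scans, only the category sequence matters.

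**Result by sequence** (UE = unable to evaluate)

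| Overall time point responses | BOR as written | BOR if SD or better qualifies |
|---|---|---|
| PR only | NE | SD |
| PR, UE | NE | SD |
| UE, PR | NE | SD |
| PR, PD | PD | SD |
| PR, UE, PD | PD | SD |
| UE, PR, PD | PD | SD |
| PR, SD | SD | SD |
| SD, PR | SD | SD |
| SD, PR, PD | SD | SD |
| PR, SD, PD | SD | SD |

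All 5 × 5 × 5 = 125 three-visit sequences of CR, PR, SD, PD and UE were enumerated, each cut at its first PD. Seventeen distinct patterns contain an unconfirmed PR and no CR. As written, 11 give SD, 3 give PD and 3 give NE. Every one of the 11 contains an SD time point and none of the other 6 does. These are counts of patterns, not of patients. Patterns with CR were left out of the 17 because SAP 7.5.1 does not say how a CR followed only by PR is to be treated.

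**Effect on ORR.** Membership of the confirmed CR/PR group is the same under both rules in all 125 sequences.

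**Non-CR/non-PD.** Appendix E gives this overall response when there is no target lesion, non-target disease persists and there is no new lesion. It is neither SD nor a response, so Non-CR/non-PD then PD is PD as written, and Non-CR/non-PD alone is NE. BIRC can return it. Entry requires "Measurable disease per RECIST 1.1 as determined by the Investigator", whereas BIRC selects its own target lesions using prior radiation history (Protocol 5.8.6.2). Appendix E treats previously irradiated or locally treated lesions as not measurable. SAP 5.5 plans a yes/no summary of measurable disease for both investigator and BIRC.

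**The case against.** The strongest objection is that no planned output is shown to be wrong. SAP 7.5.1 lists ORR by arm, its difference, an odds ratio, confidence intervals and waterfall plots. Neither SAP 7.5 nor the endpoint lists name a BOR frequency table or a disease control rate. This stands and holds the severity down. It does not remove the point: the 21-day SD condition has no role in ORR and matters only if the lower categories are used.

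Second, BOR is said to follow RECIST 1.1, and the published guideline may settle unconfirmed responses. That cannot be checked here. The supportable statement is that neither the SAP nor the adapted text in Appendix E supplies a mapping, while the SAP's own sentence points to PD or NE.

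Third, the SD sentence might be meant only as a minimum time before SD can be assigned. That is a possible intention, but the text asks for a time point of SD, so rewording is still needed.

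Fourth, SAP 7.1.1.1 can be taken to equate Non-CR/non-PD with SD. It does so only to define an adequate assessment. Measurable disease at entry should also keep such cases to disagreements between BIRC and the investigator.

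A reader might go further in four ways that the documents do not support:
- That every unconfirmed CR or PR becomes PD or NE. A subject with a qualifying SD time point is SD.
- That efficacy inference is affected. ORR and DOR (SAP 7.5.4) use confirmed responders only, and PFS and OS do not use BOR.
- That the combination arm is favoured. There are no data on direction. If that arm has more first responses, the rule would count against it.
- That mRECIST response is expressly covered. SAP 7.5.5 refers to Sections 7.1.1.3 and 7.4, so its link to 7.5.1 is only inferred.

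**Conclusion.** The point holds as a minor defect. As written, SAP 7.5.1 places a subject with an unconfirmed CR or PR, and no SD time point at 21 days or later, in PD or NE. It also leaves Non-CR/non-PD without a category. The consequence is limited to the split between SD, PD and NE and to any summary drawn from it.

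The number of subjects cannot be estimated. One could assume that 2% to 6% of the 248 planned combination subjects in the PITT population are affected, which gives 248 × 0.02 = 5 to 248 × 0.06 = 15. Nothing in the documents supports that rate. Planned accrual to the combination and sorafenib arms of 30 × 3/4 = 22.5 per month over 6 weeks (42/30.4375 = 1.38 months) gives about 31 subjects due only one scan at the cut. That is not a count of misclassified subjects, since only first-scan responders among them would matter. SAP section 3 moreover describes the 837-subject global population as already enrolled, so steady accrual up to the cut is not established.

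The conclusion rests on a literal reading of the SD sentence and on there being no other BOR mapping in the two documents.

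**What to change.** Replace the SD sentence in SAP 7.5.1 with a rule to this effect: *a subject without a confirmed CR or confirmed PR is classified SD if any overall time point response dated 21 days or more after randomization, and before PD or a PFS censoring event, is SD, an unconfirmed CR or PR, or Non-CR/non-PD.* Apply it to both BIRC and investigator BOR. Correct the cross-reference in SAP 7.5.5 so that mRECIST response follows Section 7.5.1.

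The cost is one sentence, one cross-reference and a line of derivation code. No new data are needed, and neither alpha nor confirmed ORR is touched. SAP 4.9 already provides for clarifications by addendum.

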7.1.1.4 Primary Definition

For the primary analysis directed toward the primary estimand, duration of PFS is defined as the time from randomization to the earlier of either the date of radiographic progression per BIRC or the date of death due to any cause.

PFS (months) = (earliest date of progression, death, censoring – date of randomization + 1)/30.4375

General censoring rules for the primary analysis of PFS are described below, with details provided in Table 7Table 8 (analysis ID PFS-EP-1):

- Subjects who receive systemic or local NPACT or non-protocol radiation therapy (other than to bone) or surgery to resect target lesions before experiencing an event will be right censored at the date of the last tumor assessment prior to the date of initiation of subsequent therapy/surgery. If there is no such tumor assessment post randomization, the subject will be right censored on the date of randomization.
- Subjects who have not experienced an event (and are not otherwise censored) at the time of data cutoff will be right censored on the date of their last tumor assessment post randomization that is on or prior to the data cutoff date. If there is no such tumor assessment post randomization, the subject will be right censored on the date of randomization.
- Subjects who miss 2 or more scheduled tumor assessments followed by an event will be right censored on the date of their most-recent tumor assessment prior to the missing assessments. If there is no such tumor assessment post randomization, the subject will be right censored on the date of randomization.

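### The waterfall plot rule in SAP 7.5.1 drops the progression scan and, for censored subjects, the last valid scan, so the plot matches neither its own inclusion rule nor the best overall response window

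*SAP*

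**What the plan says.** SAP 7.5.1 plans "Waterfall plots displaying maximum percent tumor reduction since baseline in target lesions", per BIRC. On who is shown, it says: "These plots will include subjects with a tumor assessment at baseline and at least one post-baseline visit". The sentence that comes next takes out of every individual series "data on or after the progression/censoring date of the respective PFS analyses", which points back to SAP 7.1.1.

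The dates come from SAP 7.1.1:

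- Progression (7.1.1.1): "The recorded date of radiographic progression is the date of the tumor assessment visit at which progression is declared". Where imaging for one visit was spread over several days, "the earliest scan date within the set will be chosen as the progression date".
- Censoring with no event at cutoff (7.1.1.4): everyone in this group "will be right censored on the date of their last tumor assessment post randomization that is on or prior to the data cutoff date".
- Censoring for subsequent therapy or surgery (7.1.1.4): anyone affected "will be right censored at the date of the last tumor assessment prior to the date of initiation of subsequent therapy/surgery".
- Two or more missed assessments before an event (7.1.1.4 and Table 8): censored at the last assessment before the gap.
- No post-randomization assessment: censored at randomization.

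Best overall response, also in 7.5.1, takes the best category which "occurs through the first overall time point response of PD and prior to any of the censoring events", the latter being those of PFS-EP-1.

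**The concern.** A cut at a date that is itself a scan date normally keeps that scan, because it is the last valid observation. Here the cut removes it. Two inconsistencies follow within one section.

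First, a subject with a baseline scan and one post-baseline scan meets the inclusion sentence. If progression or censoring falls on that scan, the exclusion sentence leaves nothing to draw. A programmer cannot satisfy both.

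Second, the figure and the response table beside it use different data. A first-scan progressor is classified as progressive disease in best overall response but has no bar. The last scan before the start of subsequent therapy counts toward best overall response but not toward the plot.

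At stake is whether a reader of the report can take the waterfall plot as a picture of all subjects with post-baseline imaging, and can reconcile it with the response table.

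**Working it through.** **Step 1. Which scan is removed.** Setting the exclusion rule against the dates in SAP 7.1.1 and Table 8 (PFS-EP-1):

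| Subject | PFS date | Scan lost |
|---|---|---|
| BIRC progression | progression visit, earliest scan date | the whole progression visit |
| Ongoing at cutoff | last adequate assessment | that assessment |
| Subsequent therapy or target resection | last adequate assessment before it | that assessment |
| Two or more missed assessments, then an event | last adequate assessment before the gap | that assessment |
| Death without progression, not censored | date of death | none; all scans precede it |
| No post-randomization assessment | randomization | none available |

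**Step 2. Effect on the bar.** The plot shows the maximum reduction. For a subject still plotted, removing a scan can only leave the bar unchanged or show less shrinkage. Hypothetical series of percent change in target lesions:

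| Series | Rule as written | Scan on the date kept |
|---|---|---|
| Progression at scan 1: +35 | no bar | +35 |
| Progression at scan 3: -10, -20, +5 | -20 | -20 |
| Ongoing, censored at scan 3: -10, -25, -40 | -25 | -40 |
| Ongoing, one scan: -15 | no bar | -15 |
| New-lesion progression at scan 2: -12, -30 | -12 | -30 |

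The first row removes an unfavourable bar. The third, fourth and fifth hide shrinkage. The second is unaffected.

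**Step 3. Size of the first-scan loss.** The documents give no figure for this, so what follows is an illustration. Inputs: medians of 3.6 months (sorafenib) and 6.0 months (combination), exponential, from SAP 2.3; scans every 6 weeks with a 7-day window, from Protocol 5.8.6.2; a month of 30.4375 days, from SAP 4.

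The planning inputs reproduce the SAP's event count: with HR 0.6, two-sided alpha 1%, 90% power and 2:1 allocation, Schoenfeld's formula gives 257 events, and power at 257 is 90.05%.

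The share with a PFS event by time t is 1 - 2^(-t/median). At 6 weeks, t = 42/30.4375 = 1.38 months:

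- Sorafenib: 1 - 2^(-1.38/3.6) = 23.3% (19.9% at 5 weeks, 26.7% at 7 weeks); 0.233 × 124 = about 29 PITT subjects.
- Combination: 1 - 2^(-1.38/6.0) = 14.7% (12.4% to 17.0%); 0.147 × 248 = about 37 PITT subjects.

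These shares include deaths before the first scan. Such subjects have no bar under any rule, so the shares are upper bounds for loss through first-scan progression. As a rough split, the same formula with the planning OS medians (12.3 and 17.8 months, SAP 2.3) gives deaths by 1.38 months of about 7.5% and 5.2%. That leaves 23.3 - 7.5 = about 16% and 14.7 - 5.2 = about 9.5%, assuming a constant death hazard from randomization.

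**Step 4. Size of the censored-scan loss.** With exactly 257 events among 372 PITT subjects, 372 - 257 = 115 (31%) are censored. Each of them with a post-randomization assessment loses the last valid scan. How many bars change depends on whether that scan was the deepest, or the only one, which the documents cannot tell us.

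**The case against.** The strongest reply is that this is one descriptive figure. SAP 7.5 treats results for the additional endpoints as supportive. Best overall response is a category and the waterfall is a continuous target-lesion display, and the SAP nowhere says that they must share a data window. First-scan progressors are still classified as progressive disease and stay in the ORR denominator, so no estimate hides them.

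Most of this stands, and it limits the severity. It does not remove the conflict between the inclusion and exclusion sentences, which concern the same plot, and the SAP gives no reason for the different window.

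A reader might infer that the rule makes tumour shrinkage look better than it is. The documents do not support that as a general statement. Only the loss of first-scan progressors works in that direction; for retained subjects the rule can only understate shrinkage, and it can also remove a censored subject who was shrinking. A reader might also infer that the rule favours the combination. Under the planning medians a larger share of sorafenib subjects is lost at the first scan, so the flattering component would help the control arm's picture.

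**Conclusion.** The point holds as a minor specification error. As written, the rule drops the progression visit and, for censored subjects with a post-randomization assessment, the last valid scan. It conflicts with the plot's own inclusion sentence and does not match the best overall response window.

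The net direction of distortion is undetermined. The 23% and 15% should not be read as the expected number of missing bars: they are upper bounds for first-scan progression only, conditional on exponential PFS with the planning medians and a first scan at 6 weeks. They also leave out subjects whose only scan is a censoring scan. Nothing here reaches ORR, PFS, OS or the alpha allocation.

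**What to change.** Reword the exclusion in SAP 7.5.1 by visit: exclude only assessments after the progression or censoring assessment visit, and keep all scans belonging to that visit.

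Replacing on-or-after with after, by calendar date, is not quite enough. SAP 7.1.1.1 takes the earliest scan date of a multi-date visit as the progression date, and Protocol 5.8.6.2 allows a chest CT with an abdomen/pelvis MRI. If those fall on different days, a date-based rule could still drop the later scan, possibly the one with the liver targets.

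Add a footnote to each plot giving, by arm, the number of subjects with no plottable value and the reason.

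The cost is a sentence and a footnote. SAP 4.9 already provides for clarifications and minor corrections by addendum before the final analyses. No data collection, sample size or inferential test changes.
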